3.1. Clinical Study

This is a single-site, non-randomized, non-controlled study at UT Southwestern Medical Center at Dallas in the Department of Plastic Surgery designed to follow up to 30 qualified and consenting subjects receiving

f1927 treatments under an IRB approved protocol

[REDACTED]

[REDACTED]

[REDACTED]

[REDACTED]

These patients will receive treatment using a f1927 device and will be treated twice over the affected areas, once each month for a total of two months, followed by two follow-up visits at 1-month and 3-months post-treatment.

[REDACTED]

[REDACTED]

[REDACTED]

[REDACTED] A quantitative assessment of the effects of treatment will be performed using VISIA and Vectra H2 3D facial skin analysis at 1-month and 3-months post-treatment.

[REDACTED]

[REDACTED]

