3.2. Primary Endpoints

- Assessment of improvement in overall facial hyperpigmentation using quantitative measurements provided by VISIA and Vectra H2 3D analysis of photos obtained at Baseline, 1-Month and 3-Months post-treatment to evaluate the efficacy of f1927 treatments
 - Calculate percent change from baseline in visualization and numeric analysis of brown and red areas utilizing the Facial Skin Analysis on Canfield's Imaging Systems
- Clinician assessment of pigmentation improvement using the Physician's Global Assessment Scale

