7.3. Screening: Visit 1 (Day 0; -14 to 0 days)

The purpose of the study, eligibility criteria and potential risks will be discussed with the potential subject.

This visit will take 30-45 minutes. Screening (Visit 1) may be combined with Visit 2.

7.4. Treatment Visits: Visit 2 (Day 0; +/-3 days) and Visit 3 (Day 30; +/-3 days)

A member of the study team will record concomitant medications and will ask subjects if they have experienced any changes in their health since the previous visit. If an adverse event (AE) is reported than the Investigator will be informed, and an AE log will be completed/updated for PI review.

The procedure will then be performed in our Plastic Surgery clinic following standard of care procedures. A trained staff member will apply a topical triple anesthetic (benzocaine, lidocaine, tetracaine) to anesthetize the areas being treated. [REDACTED]

Appropriate post-treatment care instructions will be provided as deemed appropriate by the Investigator or study staff. [REDACTED]

These visits will take approximately 1 hour.

7.5. Follow-Up Visits: Visit 4 (1-Month Post Treatment) and Visit 5 (3-Months Post Treatment)

At a minimum, all subjects will return for follow-up visits at 1 month (+/- 3 days) and 3 months (+/-3 days) after treatment.

The following activities will be performed on all study subjects during the follow-up visits:

1. The physician or study staff will ask subjects if they have experienced any changes in their health since the previous visit. Changes will be recorded accordingly. If an adverse event (AE) is reported than the Investigator will be informed, and an AE form will be completed.
 2. Subjects will acclimate to ambient temperature and humidity conditions for 15 minutes prior to any procedures being done.
 3. The physician or study staff will perform an examination of the skin in the treatment area
 4. Obtain post-treatment close up and standard photography as described in section 8.1.
 5. Obtain post-treatment photographs and measurements using the Vectra H2 3D Imaging System and VISIA Imaging System as described in section 8.1.

These visits will take about 30 minutes.

8. Assessments

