8.2 Physician's Global Assessment

Trained clinician reviewers will use the Physician's Global Assessment Scale to evaluate subject's clinical photography and assess melasma response to f1927 laser treatment. [REDACTED]

[REDACTED]

Table 1. Physician's global assessment

Score	Description
0	Clear, except for possible residual discoloration
1	Almost clear, very significant clearance (c. 90%); only minor evidence of hyperpigmentation remains
2	Marked improvement, significant improvement (c. 75%); some disease evidence of hyperpigmentation remains
3	Moderate improvement, intermediate between slight and marked improvement; c. 50% improvement in appearance of hyperpigmentation
4	Slight improvement, some improvement (c. 25%); significant evidence of hyperpigmentation remains
5	No improvement; hyperpigmented condition unchanged
6	Worse; condition worse than at week 0

9. Statistical Methods of Analysis

[REDACTED]

[REDACTED]

[REDACTED]

[REDACTED]

The primary outcome of effectiveness will be a paired comparison of baseline to all applicable post-baseline time points for hyperpigmentation and melasma severity using data obtained from Vectra H2 3D imaging results.

A descriptive statistical summary will be provided for the VISIA, Vectra H2, and Physician's Global Assessment Scale. The descriptive statistical summary includes the number of observations (N), mean, median, and standard deviation (SD), minimum (MIN) and maximum (MAX) values at all applicable time points.

The following will be calculated and reported for each evaluation parameter at the applicable post-baseline time point(s):

$$\text{Percent Mean Change from Baseline} = \frac{(\text{Visit Mean Score} - \text{Baseline Mean Score}) \times 100}{\text{Baseline Mean Score}}$$

For each new measurement set we will conduct a repeated measures of analysis of variance to detect difference between sample distributions. If differences are detected, we will subsequently evaluate specific pairwise comparisons among the post treatment visit times using a paired T-test or Wilcoxon signed-rank tests. All statistical tests will have a significance level alpha =0.05. P-values will be reported to 3 decimal places (0.000).

10. Potential Risks

Blistering, burning, scaling and infection (Rare)

Bruising (Rare)

Transient edema and/or erythema (Common)

Skin roughness and/or peeling (Common)

Pigmentary changes (Rare)

Eye injury (Rare)

Scarring (Rare)

Allergic reaction (Rare)

Photography

11. Adverse Events

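### The repeated-measures ANOVA that gates the paired tests needs all three images per subject; one mixed model on every observed image would be better for the Vectra and VISIA measures

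*Combined protocol and SAP*

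**What the plan says.** Section 3.1 describes a single-arm study "designed to follow up to 30 qualified and consenting subjects". The imaging endpoint in Section 3.2 uses "photos obtained at Baseline, 1-Month and 3-Months post-treatment", so each subject should supply three images. Section 7.5 expects that "all subjects will return for follow-up visits at 1 month (+/- 3 days) and 3 months (+/-3 days) after treatment".

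Section 9 has two analysis steps for these measures.

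- An omnibus test: "For each new measurement set we will conduct a repeated measures of analysis of variance to detect difference between sample distributions".
- If it detects a difference, "we will subsequently evaluate specific pairwise comparisons among the post treatment visit times using a paired T-test or Wilcoxon signed-rank tests".

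The same section defines the main effectiveness analysis separately: "The primary outcome of effectiveness will be a paired comparison of baseline to all applicable post-baseline time points", using the Vectra data. It also plans descriptive summaries with N at each time point, and a percent change of visit means from the baseline mean. On error rate it says "All statistical tests will have a significance level alpha =0.05".

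The visible text names no mixed model, imputation method, analysis set or dropout allowance. Several blocks at the start of Section 9 are redacted and could contain such a rule.

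**The concern.** A repeated-measures ANOVA in its usual form works on complete rows. A subject without the 3-month image leaves the test entirely, taking a valid baseline and 1-month image along. The paired tests that follow need only two images, so they can include that subject. The gate and the comparisons it opens may therefore rest on different people, and a gate weakened by lost subjects can block a comparison that more subjects would support.

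A second problem lies in the paired tests themselves. If subjects with a poor 1-month result are less likely to return, those seen at 3 months are a favourable selection. The study's hypothesis is improvement from baseline, and there is no control arm in which such selection would show.

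**Working it through.** **Inputs from the documents.** At most 30 subjects (Section 3.1); three imaging time points (Sections 3.2 and 7.1); ANOVA followed by paired tests, alpha 0.05 (Section 9). The visible text gives no dropout rate, SD, effect size or power figure, so there is no stated figure to reproduce. Everything below about dropout and variability is assumed. I also take the gated pairwise tests to include the comparisons with baseline; the literal wording mentions only post-treatment visits.

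**1. Does the method need complete rows?** A standard routine (AnovaRM in statsmodels), given 30 subjects by 3 visits with 1 of 90 values removed, refuses to run and reports unbalanced data. The analyst must drop the subject or choose another model.

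**2. Subjects in the gate and in each pair.** Let q be the chance of missing each follow-up, independently, with baseline always present. The gate keeps 30(1-q)² and each baseline pair keeps 30(1-q).

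| q | Gate | Each pair | Standard-error ratio, 1/√(1-q) |
|---|---|---|---|
| 5% | 30 × 0.9025 = 27.1 | 28.5 | 1.026 |
| 10% | 30 × 0.81 = 24.3 | 27.0 | 1.054 |
| 20% | 30 × 0.64 = 19.2 | 24.0 | 1.118 |

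The pattern of misses matters. If subjects who leave never come back, everyone seen at 3 months was also seen at 1 month. The gate then equals the 3-month pairs, and only the 1-month data of later leavers are lost. With 20% missing month 3 alone, the gate has 24, the 3-month pairs 24 and the 1-month pairs 30.

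**3. Bias when poor 1-month responders miss month 3.** This is a different dropout pattern from step 2: only the 3-month image is lost. Assumed model on the log scale: between-subject SD 0.5; response with mean -0.15 and SD 0.15, shared by both follow-ups; per-visit error SD 0.14. The true change at both visits is exp(-0.15) - 1 = -13.9%. The odds of missing month 3 rise 2.7-fold per SD of poorer 1-month change. Results are means over repeated simulated trials of 30.

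| Estimate | 10% missing | 20% missing |
|---|---|---|
| 1 month, available pairs | -13.9% | -13.9% |
| 1 month, only subjects with all three images | -15.9% | -17.5% |
| 3 months, available pairs (same subjects as complete rows) | -15.3% | -16.4% |
| 3 months, likelihood on all images | about -14.0% | about -13.9% |

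Hand check of the third row. The variance of a change is 0.15² + 2 × 0.14² = 0.0617. The covariance of the 1- and 3-month changes is 0.15² + 0.14² = 0.0421. The slope is 0.0421/0.0617 = 0.68, so about 68% of the selection on the 1-month change carries over to month 3.

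- 10% missing: ln(0.841) = -0.173, a shift of -0.023. Then -0.15 - 0.68 × 0.023 = -0.166, or -15.3%.
- 20% missing: ln(0.825) = -0.192, a shift of -0.042. Then -0.15 - 0.68 × 0.042 = -0.179, or -16.4%.

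**4. If dropout depends on the unseen 3-month result.** In a standardised model (SD 1, true change -0.50, about 21% missing month 3), the paired 3-month estimate is -0.74 at between-visit correlation 0.5 and -0.69 at 0.7. Likelihood on all images gives -0.67 and -0.64. It removes 0.07 of a bias of 0.24, and 0.05 of 0.19. With 20% missing completely at random, all methods average about -0.50 and only precision is lost.

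**The case against.** A reader might infer that one missed visit removes a subject's data from the reported results and that the planned estimates overstate improvement at both visits. The documents do not support that. The ANOVA supplies a gating p-value only. The effect is reported through paired comparisons, per-visit summaries and the percent change of visit means: "The following will be calculated and reported for each evaluation parameter at the applicable post-baseline time point(s"). A subject who misses month 3 still contributes a 1-month pair, and that estimate is unbiased in step 3. The -15.9% and -17.5% figures describe complete rows, which the plan does not say it will report. At 3 months the available pairs and the complete rows are the same people, so that bias comes from the dropout and not from the ANOVA. The plan's ratio of visit means, taken against the baseline mean of all subjects, moves less: about -14.5% and -15.2% in the same scenario on the log scale. All of this stands and limits the point.

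The text does not say that incomplete subjects are dropped, does not exclude a mixed-model implementation, and may address missing data in redacted blocks. This also stands; the conclusion is conditional on the ordinary form of the test and on the visible text.

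Nothing in the documents shows that missed visits are likely. Section 5.4 requires willingness to complete the study and excludes those thought unlikely to stay. That lowers the expected loss but does not say what happens when an image is missing.

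Finally, the near-exact recovery by likelihood in step 3 follows from letting dropout depend on an observed value. Step 4 shows the limit.

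**Conclusion.** The point holds in a limited form and is worth a change of method. Two separate effects are involved.

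- **The gate.** Run on complete rows, it loses 1.4/2.7/4.8 of 30 subjects relative to each pair at 5/10/20% independent misses. If leavers never return, the gap exists only against the 1-month pairs.
- **The 3-month paired estimate.** It overstates improvement by 1.4 percentage points (15.3 - 13.9) with 10% missing and 2.5 points (16.4 - 13.9) with 20% missing, if poor 1-month responders stay away as assumed. The ANOVA does not cause this, so repairing the gate alone would not cure it.

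The 1-month paired estimate is not biased by later dropout. The sizes rest on assumed dropout rates, an assumed dropout mechanism and assumed variances; the direction needs only that poor responders return less often. With complete attendance neither effect arises.

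**What to change.** For the Vectra and VISIA measures, replace the ANOVA and the separate paired tests with one linear mixed model fitted by REML to all observed images. Use visit as a categorical effect, unstructured within-subject covariance and small-sample degrees of freedom. Take the baseline-to-1-month and baseline-to-3-month contrasts, with 95% confidence intervals, from this model.

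State the analysis set. Report the completers-only or available-pairs result as a sensitivity analysis; the planned Wilcoxon test can be kept there, since the mixed model has no rank-based counterpart. Add a second sensitivity analysis for dropout that depends on the unseen 3-month result.

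The Physician's Global Assessment is scored only after treatment (Section 7.1), has no baseline value and is outside this change.

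The cost is SAP wording and standard software, with no extra visits. The model assumes data missing at random given earlier images, removes bias from outcome-driven dropout only in part, and gains almost nothing about change from a subject with a baseline image alone. If a redacted block already sets a missing-data rule, reconcile it with this text.

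### Sections 3.2 and 9 disagree on the primary endpoint, no colour measure or visit is named as decisive, and every test is run at 0.05 with no visible adjustment across measures

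*Combined protocol and SAP*

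**What the plan says.** Section 1 hypothesises a statistically significant improvement in the appearance of hyperpigmentation relative to baseline. Three parts of the plan bear on which test would show it.

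- **Section 3.2 (primary endpoints)** calls for assessment "using quantitative measurements provided by VISIA and Vectra H2 3D analysis of photos obtained at Baseline, 1-Month and 3-Months post-treatment", including percent change in the "numeric analysis of brown and red areas". It also lists the PGA. Nothing in the list is ranked.
- **Section 9 (primary outcome)** is narrower: "The primary outcome of effectiveness will be a paired comparison of baseline to all applicable post-baseline time points". The quantities are the severity of pigmentation and of melasma, and the only data source named is Vectra H2. VISIA and the PGA are not part of that sentence.
- **Section 9 (testing)** continues: "For each new measurement set we will conduct a repeated measures of analysis of variance". If that detects a difference, pairwise comparisons among the post-treatment visits follow, "using a paired T-test or Wilcoxon signed-rank tests". The level is then fixed: "All statistical tests will have a significance level alpha =0.05".

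Imaging is taken before treatment and at 1 and 3 months after it, so each measure has two comparisons with baseline. The visible text does not choose a colour or a visit, give the sidedness of the tests, or say whether one positive result is enough. Several lines at the start of Section 9 are redacted.

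**The concern.** The study has a single arm and follows up to 30 subjects, so its efficacy claim rests on before-after tests. If several tests are each run at 0.05 and any one may be presented as the improvement, the 5% level describes each test but not the trial's claim. The disagreement between Sections 3.2 and 9 adds to this, because it leaves open how many measures count as primary.

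The role of the ANOVA is also unclear. Section 9 defines the primary outcome as a "paired comparison of baseline to all applicable post-baseline time points". The tests that follow a positive ANOVA are described differently, as comparisons among post-treatment visits. The primary comparison can therefore be read as behind the ANOVA or as independent of it, and the two readings give different error rates.

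**Working it through.** **Plan's own figure.** The documents give 0.05 per test and no overall error rate. One test at 0.05 gives 5% in either direction, and 2.5% in the direction of improvement if two-sided.

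**Inputs from the documents**
- Level 0.05 for every test (Section 9).
- Up to 30 subjects (Section 3.1); n = 30 is used.
- Two post-treatment imaging visits (Sections 3.1, 3.2 and 7.1).
- Two imaging systems and two colours (Section 3.2).

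**Assumptions**
- Both colours are measured on both systems, giving 2 × 2 = 4 measures and 4 × 2 = 8 comparisons with baseline. Vectra H2 alone gives 2 measures and 4 comparisons.
- Tests are two-sided and data are normal.
- Correlation between measures is 0 to 0.8.
- Correlation between any two visits is 0.5.
- The PGA is left out, because the procedures table gives it no baseline score.

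**Reference values for k independent tests**
- Either direction, 1 − 0.95^k: 18.5% for k = 4 and 33.7% for k = 8.
- Improvement only, 1 − 0.975^k: 9.6% for k = 4 and 18.3% for k = 8.

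The real tests are not independent, since the two visits share a baseline and the measures come from the same face. The null case was therefore simulated: no change at any visit, paired t-tests of each visit against baseline, with and without the requirement that the measure's repeated-measures ANOVA first reach 0.05. The entries are the chance of at least one false significant comparison with baseline.

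| Measures | Correlation between measures | Either direction, ANOVA first | Either direction, no ANOVA step | Improvement only, ANOVA first | Improvement only, no ANOVA step |
|---|---|---|---|---|---|
| 4 | 0 | 16% | 32% | 8% | 17% |
| 4 | 0.5 | 13–14% | 27% | 7% | 14% |
| 4 | 0.8 | 10% | 20% | 5% | 10% |
| 2 (Vectra H2) | 0 | 8% | 17% | 4% | 9% |
| 2 (Vectra H2) | 0.8 | 7% | 14% | 3% | 7% |
| 1 | n/a | 4% | 9% | 2% | 4–5% |

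The nominal value is 5% for the either-direction columns and 2.5% for the improvement-only columns. The last row shows what the ANOVA step achieves: it keeps error near nominal within one measure. The rows above show what it does not do, which is control error across measures.

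**Sensitivity**
- If the 1-month and 3-month values correlate at 0.8 instead of 0.5, sphericity fails and the uncorrected ANOVA protects less. Four measures then give 13–22% with the ANOVA first and 18–28% without it in either direction. For improvement only they give 7–11% and 9–15%.
- If tests are one-sided at 0.05 with no ANOVA step, four measures give about 18–31% false improvement, against a nominal 5%.

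**The case against.** A reader might infer that nothing is ranked first. Section 9 does not support that: it puts Vectra H2 first. What is missing is a ranking of colour and visit within Vectra H2, and agreement with Section 3.2.

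A reader might also take the 32% as the chance of a false improvement. It is not. It counts false worsening too, ignores the ANOVA step, and needs four uncorrelated measures. With two-sided tests the matching improvement-only figure is 17%, or 8% with the ANOVA first.

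The strongest case for the plan combines these points. On Section 9's own primary outcome, with the ANOVA first, the chance of false improvement is only 3–4%, not far above 2.5%. That is correct, and on this reading the inflation is modest. It depends, however, on setting Section 3.2 aside and on placing the primary comparison behind the ANOVA, which the wording leaves open.

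Three further points stand:
- The count of four measures is an assumption. Section 3.2 does not say that both colours come from both systems, and Section 9 does not define a measurement set.
- The documents never say that a red-area result could satisfy a hypothesis about hyperpigmentation.
- The redacted lines could contain a multiplicity rule. A visible level of 0.05 is compatible with adjusted p-values judged against 0.05, so one can say only that no adjustment is visible.

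**Conclusion.** The point holds as a should-fix. Sections 3.2 and 9 conflict on what is primary, neither names a decisive colour or visit, and no adjustment across measures is visible.

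Under Section 3.2's list, read as four imaging measures, false improvement is about two to three times the nominal 2.5% if the ANOVA comes first (5/2.5 = 2; 8/2.5 = 3.2). It is four to seven times nominal if not (10/2.5 = 4; 17/2.5 = 6.8). Under Section 9's Vectra H2 outcome it ranges from slightly above nominal to about three and a half times (9/2.5 = 3.6). All of these figures rest on the stated assumptions about the number of measures, correlations, sidedness and n.

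A must-fix rating is not supported. Section 9 gives a partial ranking, its ANOVA step limits error within a measure, the most favourable reading leaves little excess, and redacted text may bear on the question.

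**What to change.** 1. Make Sections 3.2 and 9 agree on which measures are primary.
2. In Section 9, name one confirmatory test at two-sided 0.05: one Vectra H2 measure at one visit, chosen by the sponsor before analysis. Brown area at 3 months is one reasonable example; the documents do not dictate it. Test the other visit for that measure next, at 0.05, only if the first test is significant. This holds the error for the pair at 5%, or 2.5% for improvement.
3. State whether the primary comparison with baseline requires a significant ANOVA.
4. Report all other measures and visits with Holm-adjusted p-values or descriptively.

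If the sponsor prefers not to rank, apply Holm across all primary comparisons with baseline. With eight comparisons the smallest p-value is judged against 0.05/8 = 0.00625; with four, against 0.05/4 = 0.0125.

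If the redacted lines already contain such a rule, the sponsor need only confirm that it covers these comparisons.

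The cost is about one paragraph in Section 9 and a matching edit to Section 3.2, with no extra subjects, visits or measurements. The downside is that some secondary measures or visits can no longer be called significant at an unadjusted 0.05.

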3.3. Secondary Endpoints

- Monitoring incidence, severity, and relatedness of adverse events throughout the study.

4. Test Material Information

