At each visit, the Investigator will question the subject about adverse events using an open-ended question. If a potential adverse event is reported by the subject or identified during examination, directed questioning and examination will be performed when appropriate. [REDACTED]

[REDACTED]
[REDACTED]

Photographs will be taken to document any AEs if possible.

[REDACTED]
[REDACTED]
[REDACTED]
[REDACTED]

12. Subject Safety and Data Monitoring

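### Common skin reactions may be under-recorded, because the visible plan relies on an open-ended question asked about 30 days after each treatment

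*Combined protocol and SAP*

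**What the plan says.** Section 3.3 shows one secondary endpoint: "Monitoring incidence, severity, and relatedness of adverse events throughout the study".

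Section 11 gives the method, which applies at every visit: "the Investigator will question the subject about adverse events using an open-ended question". It continues: "If a potential adverse event is reported by the subject or identified during examination, directed questioning and examination will be performed when appropriate".

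Sections 7.4 and 7.5 add that, at treatment and follow-up visits, staff "will ask subjects if they have experienced any changes in their health since the previous visit". Section 7.5 also calls for an examination of the treated skin at Visits 4 and 5.

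On timing, Section 7.4 puts the two treatments at Day 0 and Day 30, each within 3 days. Section 7.5 says: "At a minimum, all subjects will return for follow-up visits at 1 month (+/- 3 days) and 3 months (+/-3 days) after treatment". The schedule in Section 7.1 marks a safety assessment at Visits 2 to 5, and has no row for a diary or for contact between visits.

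Section 10 lists "Transient edema and/or erythema (Common" among the risks. It also lists rough or peeling skin as common, without calling it transient.

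**The concern.** The endpoint needs to know who had a reaction, how bad it was and whether the laser caused it. The visible method asks a general question about a month after the laser and leaves the subject to decide what is worth mentioning. A subject who was told to expect redness or peeling may not regard it as an adverse event or a change in health. The visible text does not say whether expected reactions count as adverse events.

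A reaction that begins and ends between visits cannot be seen at the next examination. It then enters the record only if the subject brings it up, and its peak severity is known only from memory.

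The study has no control group (Section 3.1), so no comparison arm collected in the same way can offset incomplete capture. The absolute rate is the safety result, and each missed reaction lowers it. Section 1 presents limited downtime as an advantage of the treatment, so short-lived reactions bear on how the results will be read.

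**Working it through.** The plan gives no figure for adverse event capture, so there is none to reproduce. The check has three parts.

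**1. Time from each treatment to the next visit** (Sections 7.1, 7.4 and 7.5; one month taken as 30 days)

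- Treatment 1 to Visit 3: 30 − 0 = 30 days. With a 3-day window at each end, 30 ± 6 gives 24 to 36 days.
- Treatment 2 to Visit 4: 30 days after the second treatment, with one 3-day window, so 30 ± 3 gives 27 to 33 days.
- Visit 4 to Visit 5: 90 − 30 = 60 days. With both windows, 60 ± 6 gives 54 to 66 days. No treatment falls at the start of this interval.

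The interval that matters for acute reactions is therefore about 30 days, after both treatments.

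**2. Routes by which a reaction could be recorded in the visible text**

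- *Safety assessment on treatment days.* Section 7.4 describes the health-change and adverse event inquiry first and the laser procedure after it. No assessment after the laser on the same day is visible, but the text does not exclude one.
- *Inquiry at the next visit.* It covers the whole interval since the previous visit, but it is unprompted.
- *Skin examination.* Section 7.5 places it at Visits 4 and 5. None is visible for Visit 3, so after treatment 1 no planned examination is visible that could trigger directed questions. After treatment 2 it comes at about 30 days.
- *Diary, interim contact or checklist.* None appears in the Section 7.1 schedule or in the visible subject instructions in Section 6. Redacted lines in Sections 7.4 and 11 could contain one.

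**3. Illustration of direction**

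Let p be the chance of a reaction per treatment and c the share of reactions that get recorded. Both are assumptions; neither is in the documents. With two treatments treated as independent:

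- true share of subjects with a reaction = 1 − (1 − p)²
- recorded share = 1 − (1 − pc)²

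For example, p = 0.8 and c = 0.5 give 1 − (1 − 0.4)² = 1 − 0.36 = 64%, or 0.64 × 30 = 19.2 of the maximum 30 subjects.

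| p | True share | Recorded, c = 0.8 | Recorded, c = 0.5 | Recorded, c = 0.25 |
|---|---|---|---|---|
| 0.8 | 96% | 87% | 64% | 36% |
| 0.5 | 75% | 64% | 44% | 23% |

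If instead the same subjects react each time and the same subjects stay silent each time, the second treatment adds nothing. The recorded share is then p × c: at p = 0.8, 0.8 × 0.5 = 40% or 0.8 × 0.25 = 20%, against a true 80%.

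If every reaction is recorded (c = 1), there is no loss. The table shows the direction and how strongly the result depends on c. It is not an estimate for this trial.

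**The case against.** The strongest reply is that the visible text is not the whole method. Redaction in Section 11 starts directly after the sentence on directed questioning, and Section 7.4 is redacted around the procedure and the aftercare. A diary, a grading form or a rule on expected reactions could be in those lines, and text that has been blacked out is not missing from the plan. This stands, so the point must be conditional.

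The visible safeguards also count for something. The question reaches back over the whole interval, a safety assessment is marked on both treatment days, the treated skin is examined at follow-up, and the follow-up visits are a minimum. They soften the concern without removing it, for the reasons in part 2 of the working.

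A reader might infer several stronger conclusions that the documents do not support:

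- *That these reactions will certainly be under-counted.* No reaction rate, duration or recall figure is given, so a downward bias is a risk and not a demonstrated result.
- *That the recall period after treatment runs to 60 days.* The 60-day gap lies between the two follow-up visits, and neither of those is a treatment visit.
- *That all the common reactions will have cleared by the next visit.* Only edema and erythema are labelled transient. Nothing is said about how long roughness or peeling lasts.

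It can also be said that a checklist suggests symptoms, and that it leaves the month-long recall in place. Asking the open question first and reporting the two kinds of event separately deals with the first objection. The second is a real limit of the remedy.

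Finally, the study is small, no test of adverse events is visible, and these reactions are already listed as risks. That limits the consequences, but adverse event incidence and severity are still the only secondary endpoint visible in Section 3.3.

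**Conclusion.** The concern holds as a risk. In the visible text, adverse events are sought by an open-ended question, directed questions need a prior report or finding, and the next visit is about 30 days after each treatment. Common reactions may therefore be under-recorded. Severity is more exposed than incidence: an event can be remembered and reported late, but its peak cannot be observed once it has passed.

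The size cannot be computed from the documents. The illustrative figures rest wholly on assumed reaction and capture rates and should not be quoted as an expected loss. The conclusion assumes that the redacted lines in Sections 7.4 and 11 add no structured or interim collection. If they do, the point shrinks to confirming that expected reactions are counted. It should be addressed, but it does not invalidate the study.

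**What to change.** First check whether the redacted text already provides structured collection. If it does not:

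- Keep the open-ended question first at every visit.
- At Visits 3, 4 and 5, follow it with a fixed yes/no checklist of the Section 10 reactions since the previous visit, recording duration and worst severity. Visits 3 and 4 cover the month after each treatment. Visit 5 covers late or persisting effects.
- State that these expected reactions count in the secondary endpoint.
- Report solicited and unsolicited events separately.

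The cost is a one-page form and a few minutes at visits that already exist. Event rates will probably be higher and look less favourable. Severity will still be recalled over about a month, so the checklist improves capture without giving observed severity.
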